We have experience evaluating AB in smokers using RT tasks. For example, in one study we examined whether AB to smoking words, as measured by the smoking Stroop task, was associated with the motivational salience of smoking pictures, as measured by peripheral physiology [58]. Scores for the smoking Stroop and for the peripheral physiology, including zygomaticus major ("smile muscle") electromyography (EMG), corrugator supercilii ("frown muscle") EMG, heart rate (HR) and skin conductance (SC), were created by taking a difference score for each measure by subtracting the responses to the neutral from the smoking stimuli. Smokers who had slower RTs to smoking words produced larger zygomaticus major EMG to smoking cues than those with faster RTs. However, scores on the smoking Stroop were unrelated to the corrugator supercilii EMG, HR, or SC responses to smoking stimuli. These results suggest that AB to smoking cues is more strongly associated with appetitive motivational measures (i.e., zygomaticus major activity) than with measures of avoidance (i.e., corrugator supercilii activity) or measures of physiological arousal (i.e., HR, SC). This is consistent with theories that smoking cues are associated with conditioned responses that capture attention, and are consistent with other work from our lab [59,60].

We have experience assessing in-home AB in smokers trying to quit. As part of an Ecological Momentary Assessment (EMA) study, we had 119 community smokers carry around a personal data assistant (PDA) during the first week following their scheduled quit attempts [61]. As part of multiple planned and random assessments per day, participants recorded their craving to smoke and completed a modified Stroop task, a measure of AB to smoking words. Overall, the smokers produced a significant smoking Stroop effect, (17.9 ms, $SD=46.6$; $t[118]=4.19$, $p<.0001$, Cohen's $d = 0.38$), indicating AB to smoking words, and the smoking Stroop effect was positively correlated with craving ratings, $r(117)=.28$, $p<.01$. These results demonstrate that reliable and significant AB can be captured on a hand-held device in a participant's day-to-day environment, and that this AB is associated with self-reported craving.

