Study overview. Participants will be 250 community smokers, currently interested in quitting smoking, who will be randomly assigned (stratified by gender) to receive either ABM or sham training. Smokers in both groups will attend three laboratory sessions (Figure 2). The first lab session will establish each smoker's baseline smoking behavior and AB towards smoking picture and word cues by assessing reaction time (RT) and event-related potential (ERP) electroencephalography to modified dot-probe (MDP), Stroop color-word naming tasks and a passive picture viewing task. After the first lab session, participants will complete 13 days of daily in-home training (ABM or sham) and AB assessments that will be administered through a provided smartphone, with compliance and accuracy rewarded monetarily. The second lab session will occur the day after the final day of in-home training and will involve the same assessments as the first session, to gauge the short-term impact of ABM on AB and smoking behavior. At the end of the second lab session, participants will have a 30-minute counseling session with a smoking cessation counselor and be given the first half of an 8-week supply of NRT. The participants will be instructed to quit the next day, and will have 3 biweekly phone counseling sessions while on NRT. After participants complete one biweekly phone counseling session, they will be mailed the remainder of their 8-week supply of NRT. Participants will be given a window of seven days after the scheduled date of their second lab session to complete the session. The final lab session, which will occur 8 weeks after the second session, will measure the longer-term impact of training on smoking behavior and AB. Participants will be given a window of fourteen days after the scheduled date of their final lab session to complete the session. Out of window visits will be noted in the progress notes but will not be considered a protocol deviation. Visit 3 has a window with an ending period of whenever final abstinence data is collected or the trial ends, whichever is sooner. A study staff member will make attempts to contact participants who miss Visit 3 until the end of the study or until the participant requests no further efforts be made to contact them. For those who miss Visit 3, a study staff member will call them to invite them to come in as originally planned so that abstinence (e.g., TLFB assessment since last contact, CO, urine cotinine, and anabasine), and lab data can be collected. If participants are unable to attend Visit 3, staff will ask participants to complete TLFB over the telephone to record CPD since last visit. Staff also will offer to send participants' questionnaires via email. If smoking abstinence is reported, staff will invite participants to come in or will offer to send them a NicAlert or comparable urine cotinine test to biochemically verify abstinence. Participants will be asked to send a picture of the cotinine test to research staff via text message, email, or postal mail.

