Power analysis. To demonstrate that this proposal has adequate sample size to detect meaningful amplitude changes in the continuous measures taken at the post-training laboratory sessions (Specific Aims 1 & 2), we conducted a power analysis using the G*Power program (v3.1.2; Heinrich Heine University, Düsseldorf, Germany). We calculated power to ensure that we could detect a significant 2-way (ABM intervention by time) ANOVA interaction for any of our continuous measures, as assessed at the baseline, 1-day post-training, and 8-weeks post-training sessions. If we assume a conservative Bonferroni-corrected Type I error rate of $\alpha=0.01$, 250 participants, moderately correlated within-subject observations ($r=0.5$), and a conservative nonsphericity correction ($\varepsilon=0.75$) we have 80% power to detect differences corresponding to a Cohen's f of 0.11 or larger for the 2-way interaction. Even if we were to experience an unlikely 30% attrition rate, we would have power to detect a Cohen's f of 0.13 or larger. According to Cohen [117], a Cohen's f of 0.10, 0.25, and 0.40 correspond to a small, medium, and large effect size, respectively, meaning that we have the power to detect a small effect size or greater on our continuous measures. To demonstrate that we would have adequate power to detect likely AB differences for Aim 1, we searched the literature for studies with a similar design to ours. Given that no previous study has evaluated the impact of multi-session ABM on AB in

smokers, we decided to estimate a likely effect size from the one alcohol study that used the MDP task for both multi-session ABM and the AB assessments [2]. We estimated a Cohen's *f* value for this study by taking the square root of the *F* ratio multiplied by the ratio of the degrees of freedom [117]. From this formula, we estimated a Cohen's *f* of 0.64, based on the reported *F* value for the significant ABM training group (ABM, sham) main effect, $F(1,23)=9.4$, $p<.01$. This Cohen's *f* value corresponds to a large effect size and is well within the range for which we have sufficient power to detect. We recognize that this alcohol study does not provide an ideal comparison for the effects sizes we will likely obtain, but it does suggest that ABM produces large effects on AB, effects which should be well within the power requirements of our study to detect.

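### Aim 1, Stroop outcome only: on the team's own smoker data, complete removal of the bias has about 61% power at the plan's settings, so the claim of ample power is not supported

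*Combined protocol and SAP*

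**What the plan says.** Under Statistical Approach & Expected Outcomes, the Aim 1 paragraph plans a 2 (group) by 3 (session) linear mixed model on reaction-time difference scores, run separately for the modified dot-probe (MDP) and the Stroop. It predicts that bias falls with ABM and not with sham. The opening statement of aims adds that the change should still be present 8 weeks after training.

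The Power analysis section covers all continuous measures of Aims 1 and 2 together. It assumes a "conservative Bonferroni-corrected Type I error rate of $\alpha=0.01$, 250 participants", "moderately correlated within-subject observations ($r=0.5" and a "conservative nonsphericity correction ($\varepsilon=0.75". From these it states that "we have 80% power to detect differences corresponding to a Cohen's f of 0.11 or larger for the 2-way interaction", and adds: "Even if we were to experience an unlikely 30% attrition rate, we would have power to detect a Cohen's f of 0.13 or larger".

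To show that likely Aim 1 effects are covered, it takes f = 0.64 from the group main effect, F(1,23) = 9.4, in an alcohol study that used the MDP task for both training and assessment. It concedes that this study is not an ideal comparison, but concludes that "it does suggest that ABM produces large effects on AB, effects which should be well within the power requirements of our study to detect".

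Under Preliminary Studies, the protocol reports the team's own hand-held Stroop data from 119 smokers in the first week after a scheduled quit attempt: "a significant smoking Stroop effect, (17.9 ms, $SD=46.6", with Cohen's d = 0.38. The Power analysis section does not use these data.

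**The concern.** Aim 1 power is stated only as Cohen's f for an interaction and labelled a small effect. In a two-arm, three-session design an interaction f of 0.11 is nearly half a standard deviation between arms, because f averages the effect over all six cells. The plan never makes that conversion, so it does not show that the detectable difference is larger than the whole Stroop bias in its own data.

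The only effect size offered as reassurance comes from a different term (a main effect), a different task (MDP) and a different population (alcohol patients).

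The Stroop is the outcome that tests whether training carries over to another stimulus modality. The protocol notes that an earlier single-session smoking study found no such carry-over. If the Stroop comparison has modest power even for a large change, a non-significant result could be taken as absence of generalisation when the design could readily have missed it.

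**Working it through.** **Inputs**
- Alpha 0.01, N = 250, r = 0.5, ε = 0.75, 2 groups, 3 sessions, 30% attrition (250 × 0.7 = 175): Power analysis section. The Study overview describes the sample as "Participants will be 250 community smokers, currently interested in quitting smoking, who will be randomly assigned (stratified by gender") and gives no allocation ratio; 1:1 is assumed.
- Pattern of effect: fall of size d in ABM at both follow-ups, sham unchanged (aims and Aim 1 analysis paragraph).
- Stroop bias 17.9 ms, SD 46.6 ms (Preliminary Studies). Check: 17.9 / (46.6/√119) = 4.19 and 17.9/46.6 = 0.384, both as reported.

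**Step 1. Reproduce the plan's figures.** Noncentral F with λ = f²·N·3·ε/(1 − r), df1 = 2ε = 1.5 and df2 = 2ε(N − 2).
- N = 250 (df 1.5 and 372): f for 80% power = 0.1077, stated as 0.11.
- N = 175 (df 1.5 and 259.5): f = 0.1290, stated as 0.13.
- √(9.4/23) = 0.639, stated as 0.64.

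All three agree.

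**Step 2. Convert f to a difference between arms.** With ABM (0, −d, −d) and sham (0, 0, 0), the interaction effects in each arm have size d/3, d/6 and d/6. Their mean square is (1/9 + 1/36 + 1/36)d²/3 = d²/18, so f = (d/SD)/√18.
- N = 250: 0.1077 × √18 = 0.457 SD; × 46.6 = 21.3 ms (21.7 ms from the rounded 0.11).
- N = 175: 0.1290 × √18 = 0.547 SD; × 46.6 = 25.5 ms.

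**Step 3. Power for removing the bias.** Complete removal: f = 0.384/√18 = 0.0905.
- N = 250: λ = 0.0905² × 250 × 3 × 0.75/0.5 = 9.22, power 60.9%.
- N = 175: λ = 6.46, power 41.6%.
- Half the bias (8.95 ms): 11.6% and 7.6%.

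An effect present at the first follow-up only gives the same f and power. One that has half faded by 8 weeks gives 45% at N = 250.

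**Step 4. Sensitivity to alpha and ε** (r = 0.5, SD 46.6 ms)

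| Alpha | ε | Full removal, N = 250 | Full removal, N = 175 | Half removal, N = 250 |
|---|---|---|---|---|
| 0.01 | 0.75 | 61% | 42% | 12% |
| 0.01 | 1 | 73% | 52% | 14% |
| 0.025 | 0.75 | 73% | 55% | 20% |
| 0.025 | 1 | 83% | 65% | 23% |
| 0.05 | 0.75 | 81% | 66% | 28% |
| 0.05 | 1 | 89% | 75% | 33% |

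**Step 5. Sensitivity to r and SD** (alpha 0.01, ε = 0.75, full removal, N = 250): r = 0.3 gives 43% and r = 0.7 gives 87%; SD 40 ms gives 78% and SD 60 ms gives 35%.

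**The case against.** Much of the case on the other side stands.

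- **Nothing is miscalculated.** A reader might infer an arithmetic error. There is none: 0.11, 0.13 and 0.64 all reproduce. The fault lies in the conclusion drawn from them.
- **The evidence covers the Stroop only.** A reader might infer that Aim 1 as a whole is underpowered. The documents give no MDP mean or SD in ms, so that cannot be shown. The alcohol study was chosen because it used the MDP, and it keeps some relevance there.
- **The 61% rests on settings that the plan calls conservative.** The Aim 1 paragraph states no alpha. The 0.01 equals 0.05/5, matching the five continuous Aim 2 measures, whereas two Aim 1 outcomes would give 0.05/2 = 0.025. A mixed model whose only random effect is a subject intercept implies ε = 1. With both changes, full removal reaches 83% and the 80%-power effect is 17.4 ms, just under the whole bias. A focused contrast of mean post-training minus baseline at alpha 0.01 gives about 82%. But 0.01 and 0.75 are the plan's only stated figures, and it powers the omnibus interaction, not such a contrast.
- **The SD is borrowed.** It comes from repeated hand-held assessments after a quit attempt, not from one laboratory session with 80 trials per word type. The laboratory SD, mean bias and r could be better or worse. An SD near 39 ms or an r near 0.65 would bring full removal to 80% at the plan's alpha and ε.
- **Zero is not a ceiling.** A reader might infer that the trial cannot reach 80% power for any possible effect. The aims also hypothesise increased bias towards neutral cues, so scores could pass zero. Even so, 80% power at the plan's settings needs a change about 19% larger than complete removal (21.3/17.9 = 1.19) on an untrained task.
- **The plan qualifies the comparison.** It does concede that the alcohol study is not ideal, but it keeps the reassurance.

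These points soften the headline figure without rescuing the claim. In every row of the table, removing half the bias has at most about 33% power at N = 250, and full removal with 30% attrition stays below 80%.

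**Conclusion.** For the Stroop outcome, the statement that likely effects are comfortably covered is not supported by the protocol's own smoker data. At the plan's settings the 80%-power difference is about 0.46 SD, or about 21 ms against a total bias of 17.9 ms. Complete removal has about 61% power (42% with 30% attrition), and removing half has about 12%. The f of 0.64 is no evidence of power for a Stroop group-by-time interaction.

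These figures assume 1:1 allocation, a laboratory Stroop SD near 46.6 ms, r = 0.5, and a fall in ABM that persists at 8 weeks with sham unchanged. Full-removal power should be read as a range, since it exceeds 80% under some defensible settings. The low power for partial removal is the firmer result.

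A reader might go further and treat any non-significant Stroop result as inconclusive. That does not follow: a confidence interval narrow enough to exclude a meaningful reduction would be informative.

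**What to change.** 1. In the Power analysis section, restate Stroop power in SD and ms: 80% power for about 0.46 SD (about 21 ms), or about 0.55 SD (about 25.5 ms) with 30% attrition. Add the power for full and half removal of a 17.9 ms bias. Name the assumed SD and its source, and give the sensitivity to alpha, ε, r and SD shown above.
2. Limit the f = 0.64 comparison to the MDP, note that it is a main effect, and withdraw the reassurance for the Stroop.
3. Plan to report the Stroop between-arm difference in change with its confidence interval in ms. Base any conclusion of no generalisation on whether that interval excludes a meaningful reduction, not on non-significance alone.

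The cost is wording in the power section and a reporting rule for the Stroop. The stated power becomes less favourable; no extra participants are needed.

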Smoking accounts for 12% of global adult mortality. If current smoking patterns continue, by 2020 tobacco will kill about 10 million people every year [9]. One crucial step to changing this trend is to increase the long-term success of smoking cessation interventions. More than 94% of those making an unaided cessation attempt relapse within one year [10]. Even 70% of smokers who receive first-line smoking cessation therapies relapse by 6 months post-quit [1]. The high risk of relapse has been attributed to the ability of addictive drugs like nicotine to hijack the neural mechanisms that evolved to shape behaviors related to the pursuit of rewards and the cues that predict them [4,11]. Most contemporary theories of drug dependence postulate that chronic drug-users develop AB to stimuli previously associated with drug use, making the drug cues more salient than other stimuli, including intrinsically pleasant stimuli [4,6,12,13]. Evidence largely supports this postulation, as chronic users of drugs [14–16] and tobacco [17] exhibit AB to drug-related cues that is absent in nonusers. Brain imaging studies from our lab and that of others have shown that, in smokers, cigarette-related cues automatically attract attentional resources and are processed as motivationally relevant stimuli [18–23]. Additionally, decreased AB to drug-related cues has been associated with better treatment outcomes [24–28]. The theoretical and empirical support for the association between AB, substance use, and treatment outcome has led many to pursue research into directly altering AB using ABM, a computer-delivered intervention designed to reduce AB toward drug-related cues. ABM, performed over multiple sessions, has been shown to reduce AB to alcohol-related cues and to reduce long-term alcohol consumption in problem drinkers [29] and in the alcohol dependent [2,3]. The two published studies that assessed the impact of ABM on smokers found no impact of training on smoking behavior and craving, but both relied on a single training session in a laboratory [7,8], which has not been found to be effective in alcohol studies [30–32].

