To demonstrate that this proposal has adequate sample size to detect likely changes in abstinence after 8 weeks of NRT (Aim 2), we conducted a power analysis using G*Power to calculate effect size *w*, the square root of the standardized chi-square statistic [117]. Given a total sample size of 250 (missing participants will be assumed to be smoking), 1 degree of freedom, and a Type I error rate of $\alpha = 0.05$, we have 80% power to detect differences corresponding to an effect size *w* of 0.177 or larger, which means that we will have enough power to detect a difference in abstinence rates of 12.6% or higher between training groups. To estimate likely abstinence rates, we turned to the ABM and alcohol literature, because there are no published ABM and smoking studies that report abstinence outcome. In a study comparing ABM to sham treatment in 214 alcoholics, Wiers and colleagues [3] reported that 54% of those in the ABM group, and 41% in the control group, were abstinent at 1-year follow-up, a difference of 13%. Given that between-group substance-dependence treatment differences are often greatest at the end of treatment, and narrow by 1-year follow-up, we believe that we will have adequate power to detect likely differences in abstinence rates.

Potential Problems & Alternative Strategies

Participant recruitment. We expect to have no difficulty recruiting the needed number of participants. In the past 5 years, for example, our team has recruited more than 800 community volunteers for our various smoking research studies. We have had considerable success enrolling participants into studies involving RT and EEG/ERP recordings and our procedures allow us to collect highly reliable data.

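### The 12.6-point detectable abstinence difference needs a pooled quit rate of about 15%; at the 41% vs 54% the plan cites, 80% power needs 17.7 points and power is 54%

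*Combined protocol and SAP*

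**What the plan says.** The abstinence part of the Power analysis (section D, Statistical Approach & Expected Outcomes) takes three steps.

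1. It sets the inputs: "Given a total sample size of 250 (missing participants will be assumed to be smoking), 1 degree of freedom", a type I error rate of 0.05 and 80% power. From these it obtains w = 0.177 and infers that "we will have enough power to detect a difference in abstinence rates of 12.6% or higher between training groups". No control-group or pooled abstinence rate accompanies the 12.6%.
2. To gauge likely rates it turns to an alcohol trial of ABM against sham in which "54% of those in the ABM group, and 41% in the control group, were abstinent at 1-year follow-up, a difference of 13" percentage points.
3. It reasons that group differences tend to be largest at the end of treatment and to shrink by one year, and concludes that "we believe that we will have adequate power to detect likely differences in abstinence rates".

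The Aim 2 analysis paragraph of the same section specifies the test: a chi-square on the 2 x 2 table of abstinence by training group, with a higher rate expected under ABM.

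**The concern.** Cohen's w is a standardised effect. Turning it into a difference between two proportions requires the pooled proportion, and the plan makes the conversion without giving one. The reader is then invited to compare 12.6 points with 13 points as if both were on the same scale. They are not: the first figure belongs to a pooled rate near 15%, the second to one of 47.5%.

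At stake is how the cessation result is read. If the trial finds no significant difference in abstinence, the plan as written presents that as the outcome of a test with 80% power for an effect of the size it cites. If the real power at those rates is close to one half, a null result says much less.

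**Working it through.** **Inputs.** From the abstinence power paragraph: N = 250, 1 df, alpha = 0.05, 80% power, w = 0.177, and cited rates of 54% and 41%. The allocation ratio is not stated; I assume 1:1, or 125 per arm, which favours the plan because unequal arms would raise the detectable difference.

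**Step 1: reproduce w.** Power is P(noncentral chi-square with 1 df and noncentrality λ > 3.841), with λ = N·w². For 80% power λ = 7.849, so w = √(7.849/250) = 0.1772. At w = 0.177 power is 79.9%. The plan's w is correct.

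**Step 2: convert w to a difference.** In a balanced 2 x 2 table with pooled rate p̄,

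w = d / (2·√(p̄(1 − p̄))), so d = 2·w·√(p̄(1 − p̄)).

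Setting d = 0.126 and w = 0.177 gives p̄(1 − p̄) = (0.126/0.354)² = 0.1267, so p̄ = 0.149 (or 0.851). The arms are then 14.9% ± 6.3 points, or 8.6% and 21.2%. The plan states no such rate.

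**Step 3: detectable difference at 80% power, by pooled rate** (w = 0.1772)

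| Pooled abstinence rate | Detectable difference (points) |
|---|---|
| 10% | 10.6 |
| 15% | 12.7 |
| 20% | 14.2 |
| 25% | 15.3 |
| 30% | 16.2 |
| 40% | 17.4 |
| 47.5% | 17.7 |
| 50% | 17.7 |

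**Step 4: power at the cited rates.** For 54% vs 41%, p̄ = 0.475 and w = 0.13/(2·√(0.475 × 0.525)) = 0.1302. Then λ = 250 × 0.1302² = 4.24, and power is 53.9%. The two-proportion normal formula and exact enumeration of the Pearson test also give 53.9%; the arcsine approximation gives 54.1%. A one-sided 5% test would reach only 66%. For 80% power at these rates the two-proportion formula needs 231 per arm and the w formula 232.

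**Step 5: power for a 12.6-point gain, by control rate** (two-proportion formula, 125 per arm)

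| Control rate | Power |
|---|---|
| 10% | 77% |
| 20% | 62% |
| 30% | 54% |
| 41% | 51% |

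**The case against.** Four points can be made for the plan.

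*The cited rates are not the planning assumption.* They are one-year figures, and the plan argues that the difference at the end of treatment should be larger. That is a fair reading of the text. The argument is qualitative, though, and it starts from 13 points measured against a 12.6-point threshold. With sham at 41%, 80% power needs about 17.6 points by the two-proportion formula, or about 58.6% under ABM. The documents give no figure suggesting a gap of that size.

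*Smokers' quit rates may be lower than these.* At a pooled rate of about 15% or below, the 12.6-point claim is true. But the plan does not state such a rate for its participants, and if it was intended, the 41% vs 54% comparison no longer supports the claim. The Significance section says "Even 70% of smokers who receive first-line smoking cessation therapies relapse by 6 months post-quit", which suggests about 30% abstinent. That is a different time point and does not fix this trial's rate. At a 30% pooled rate the detectable difference would be 16.2 points.

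*Abstinence is not the main outcome.* The Exploratory Aims paragraph does list cessation rates, and the opening Aim 2 hypothesis names only continuous measures. Yet the analysis section places the abstinence test under Aim 2 with a predicted direction, and the power section labels its calculation Aim 2. An endpoint's rank does not excuse an incorrect power statement. The separate power calculation for the continuous measures is unaffected.

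*No one need read a null result as proof of no effect.* True; that consequence is a risk, not something the plan commits to.

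**Conclusion.** The concern holds: the statement is wrong as written. The w of 0.177 is correct, but 80% power for a 12.6-point difference is available only when the pooled abstinence rate is at or below about 15%, or at or above about 85%. At the only abstinence rates the power section cites, 80% power requires 17.7 points (17.6 by the two-proportion formula), and power for the cited difference is 54%. The conclusion of adequate power is therefore unsupported.

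This rests on 1:1 allocation and on the plan's own N, alpha and test. One-sided testing, the arcsine approximation and exact calculation do not rescue the claim at the cited rates.

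**What to change.** Replace the 12.6% sentence with text to this effect: with 125 per arm, w = 0.177 corresponds to 17.7 points at the cited rates of 41% and 54%, about 16 points at a pooled rate of 30%, and 12.6 points at a pooled rate of about 15%; power for 41% vs 54% is 54%. State the allocation ratio and, if the investigators have one, the abstinence rate they expect in the sham arm.

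Delete the conclusion that power is adequate. Add that abstinence will be reported as a risk difference with a 95% confidence interval. At 54% vs 41% the half-width would be 1.96 × √[(0.54 × 0.46 + 0.41 × 0.59)/125] = 0.123, or about 12 points, which shows the reader directly how much a null result can exclude.

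The cost is a change of wording in the power section and one reporting line. The stated power becomes less favourable; sample size and trial conduct do not change.
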